11.2.1 Efficacy Analysis Sets

11.2.1.1 Intent-to-treat Set

This set will include all randomized subjects, whether or not they receive a single dose of the study drug. Analyses will be based on the randomized treatment even if a subject inadvertently receives the incorrect drug or dosage. The reference date for consideration of endpoints is the randomization date (the times to onset of events will be calculated starting from the randomization date).

11.2.1.2 Modified Intent-to-treat Set

This set will include all randomized subjects who receive at least one tablet of the study drug. Analyses will be based on the randomized treatment even if a subject inadvertently receives the incorrect drug or dosage. The reference date for consideration of endpoints is the initial dose of study drug date (the times to onset of events will be calculated starting from the initial dose of study drug date).

11.2.1.3 Per Protocol Set

This set will include all randomized subjects who receive at least one tablet of the study drug and do not have any major protocol violations (as defined prior to unblinding of the database for final analyses). Analyses will be based on the randomized treatment even if a subject inadvertently receives the incorrect drug or dosage. The reference date for consideration of endpoints is the initial dose of study drug date (the times to onset of events will be calculated starting from the initial dose of study drug date).

11.2.2 Pharmacokinetic Analysis Set

The PK analysis set will include all randomized subjects who meet the following criteria.

- 1) Subjects in the DU-176b group.
- 2) Subjects with no major protocol violations affecting PK.
- 3) Subjects with at least one usable plasma DU-176 concentration measurement.
- 4) Subjects with usable information on administration.

11.2.3 Pharmacodynamic Analysis Set

The PD (PD indicator and biomarker) analysis set will include all randomized subjects who meet the following criteria.

- 1) Subjects with no major protocol violations affecting PD.
- 2) Subjects with at least one usable PD indicator or biomarker measurement.

11.2.4 Safety Analysis Set

This set will include all randomized subjects who receive at least one tablet of the study drug. Analyses will be based on the randomized treatment, unless a subject inadvertently receives the incorrect drug or dosage during the entire study, in which case, the subject will be grouped according to the treatment actually received. The reference date for consideration of endpoints is the initial dose of study drug date (the times to onset of events will be calculated starting from the initial dose of study drug date).

11.3 Handling of Data

Before unblinding, the Sponsor will decide on the handling of data after discussion with the medical experts, based on the criteria for the handling of data in this section, and then lock the data.

11.3.1 Handling of Protocol Deviation Data

Before the database is locked, the Sponsor will confirm with the expert about the cases to be analyzed and the criteria for handing the data for analysis, and will discuss and decide on the handling of problems not specified at the planning stage, and prepare records of these decisions.

11.3.2 Handling of Survey and Measurement Times

The eligibility assessment period will be within the 30 days after the day of informed consent, which will be counted as Day 0. The window for surveys and measurements

for each visit will be within 14 days before or after the specified date, which will be considered Day 0. The window for the examination at completion of study treatment will be 60 days after the date of declaration of completion of the study, which will be considered Day 0. The window for the examination at discontinuation will be 7 days after the day of discontinuation, which will be considered Day 0. The window for the final follow-up will be 30 to 37 days after the day of the examination at completion of study treatment, which will be considered Day 0 (For subjects who continue the study treatment after the completion of study treatment, in principle, within a month from the day of notifying their study treatment assignments as Day 0.). If multiple measurements are made within the window, the measurements made on the day nearest to the specified day of measurement will be selected. If there are measurements before and after the specified day that are the same number of days away, the latter measurements will be selected.

Data that do not meet the handling criteria will be excluded from analysis. If there are no data that meet the handling criteria, the relevant data point will be handled as being missing.

11.3.3 Handling of Missing Data

No missing data will be imputed with estimated or calculated values.

11.4 Statistical Analysis Items and Analysis Methods

11.4.1 Baseline Subject Characteristics

Distributions and summary statistics will be calculated by treatment group for baseline subject characteristics (demographic and reference ranges).

11.4.2 Efficacy Analysis

11.4.2.1 Primary Endpoint

11.4.2.1.1 Primary Analysis

For the composite endpoint of stroke and SEE observed from randomization up to the examination at completion of study treatment or the examination at discontinuation, \$\$\$\$\$\$ the time to onset of the initial event* will be compared. The treatment group will be compared based on a Cox proportional hazard model with the CHADS₂ score (≤ 2 or ≥ 3) as covariate (significance level 5%, 2-sided, confidence coefficient for estimates: 95%). If any factors affecting the primary endpoint are found in a blinded review before data are

^{§§§§§:} For subjects withdrawn from study participation

locked, these factors will also be considered as covariates.

*: This will apply to all events whether or not the subject receives the study drug. The time to onset of the initial event is defined as the time from the day of randomization to the initial event experienced by a subject. For subjects who do not experience an event during the study, the time to onset of the initial event will be censored at the day of the examination at completion of study treatment, the day of the examination at discontinuation (for subjects withdrawn from study participation) or death, whichever comes first.

11.4.2.1.2 Secondary Analysis

The cumulative incidence of events will be estimated for each treatment group using the Kaplan-Meier method. Sensitivity analysis of the events that occur during the "on-treatment" period** in the mITT analysis set and PPS will be performed.

**: "On-treatment" period is defined as the study treatment period and up to 3 days after the last dose (approximately five times the half-life [T_{1/2}] of DU-176 corresponds to 3 days). If the subject resumes study drug, the subject is considered at risk again. However, in analysis, a subject who has received the study drug up to the examination at completion of study treatment will not be considered at risk after the day of the examination at completion of study treatment, and events that occur on or after the day of the examination at completion of study treatment will not be included in analysis. For subjects who do not experience an event while at risk, the time to onset of the initial event will be censored at 3 days after the final dose, the day of the examination at completion of study treatment, the examination at discontinuation (for subjects withdrawn from study participation), the day of the subject's last assessment, or death, whichever comes first.

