From the safety standpoint, no hemorrhagic stroke was found during administration of edoxaban at 15 mg once daily in the ENGAGE AF-TIMI 48 study, and the annual incidence of intracranial hemorrhage was 0.14%/year, lower than the incidence in the warfarin group of 1.26%/year, and also lower than the incidence of 0.57%/year in subjects administered edoxaban at 30 mg once daily due to dosage adjustment. The annual incidence of major bleeding was 1.50%/year with administration of edoxaban at 15 mg once daily, which was lower than the incidences of 4.85%/year in the warfarin group and 3.05%/year with administration of dosage-adjusted edoxaban at 30 mg once daily. In addition, even if analysis is restricted to subjects aged 80 years or older in the ENGAGE AF-TIMI 48 study, the annual incidence of major bleeding was 1.99%/year

with administration of edoxaban 15 mg once daily, 6.77%/year in the warfarin group, and 4.28%/year with administration of dosage-adjusted edoxaban at 30 mg once daily, showing that even in elderly patients with AF, the bleeding risk from administration of edoxaban at 15 mg once daily is lower than that of warfarin or of edoxaban at the approved dosage.

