Thus, administration of edoxaban at 15 mg once daily is associated with a lower bleeding risk than the available oral anticoagulant warfarin or administration of edoxaban at 30 mg or 60 mg once daily, and from the efficacy standpoint, it is considered to be effective at reducing the risk of stroke to a certain extent. Therefore, it is considered that 15 mg of edoxaban once daily can be administered to elderly patients with AF who have not received aggressive anticoagulant therapy due to concerns about bleeding. Accordingly, we planned a randomized, double-blind, placebo-controlled study to evaluate the efficacy and safety of administration of edoxaban at 15 mg once daily in elderly patients with NVAF who are ineligible for the standard of care, oral anticoagulants, at the approved dosage due to concerns about bleeding. A composite of stroke and SEE was selected for primary efficacy endpoint, to evaluate the superiority of administration of edoxaban at 15 mg once daily in reducing the risk of stroke and SEE compared to the placebo group. Major bleeding was selected for the primary safety endpoint, and compared with the placebo group, and clinical acceptability was also assessed with reference to the incidence of major bleeding with available oral anticoagulant therapies. If this study finds that administration of edoxaban at 15 mg once daily is effective, and that its safety is clinically acceptable, it is expected to provide a new option for stroke prevention in elderly patients with NVAF who have not received aggressive treatment with standard of care.

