5.2 Study Treatments Administered

5.2.1 Dose and Route of Administration

After randomization, study treatment will be started on the same date that notification of study drug identifiers is given. One tablet of DU-176b 15 mg or placebo will be administered orally once daily. Administration of the study drug will be continued until the examination at completion of study treatment performed within 60 days after the declaration of completion of the study. Completion of the study will be declared when the planned number of subjects with primary efficacy endpoint events (stroke and SEE) has been collected. The planned mean duration of study treatment is 2 to 2.5 years. When the investigator or subinvestigator requires to know the study treatment assignment for each subject to determine the subsequent treatment after the final administration of the study drug, the study treatment can be continued until the final follow-up examination (in principle, within a month after notifying their study treatment assignments) after obtaining consent from the subject. The planned duration of the additional study

treatment from the examination at completion of study treatment to the final follow-up examination is 3 to 4 months.

<Rationale>

For the DU-176b group, a dosage of 15 mg once daily was selected, so that it is expected to be effective at reducing the risk of stroke, and so that the bleeding risk is lower than that for the approved edoxaban dosage.

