11.4.2.2 Secondary Endpoints

The following secondary endpoints will be analyzed in the same way as primary endpoints.

- 1) Composite of stroke, SEE, and death due to CV
- 2) MACE
- 3) Stroke, SEE, and all-cause mortality
- 4) Net clinical benefit: stroke, SEE, major bleeding, and all-cause mortality
- 5) All-cause mortality

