11.4.5.1 Bleeding Events

Bleeding events will be classified into the following categories and summarized by treatment group, and analyzed in the same way as the primary endpoint.

- 1) Major bleeding
- 2) Major bleeding and clinically relevant non-major bleeding
- 3) Clinically relevant non-major bleeding
- 4) Minor bleeding

****** Subjects withdrawn from study participation

5) All bleeding events

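### Kaplan-Meier with death censored is named as the estimator of cumulative incidence of stroke/SEE in patients aged 80 or older, so the reported absolute risk is too high in each arm

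*Combined protocol and SAP*

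**What the plan says.** Section 11.4.2.1.2 sets out the descriptive analysis of the primary endpoint: "The cumulative incidence of events will be estimated for each treatment group using the Kaplan-Meier method". The footnote to section 11.4.2.1.1 gives the censoring rule for subjects without an event. They are censored at the completion examination, "the day of the examination at discontinuation (for subjects withdrawn from study participation) or death, whichever comes first". The on-treatment sensitivity analysis in 11.4.2.1.2 also censors at death. The endpoint is stroke and SEE, so a death from another cause is not an event.

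Other endpoints refer back to this section. Section 11.4.2.2 says "The following secondary endpoints will be analyzed in the same way as primary endpoints", and section 11.4.5.1 says the bleeding categories will be "analyzed in the same way as the primary endpoint". The section referred to, "11.4.2.1 Primary Endpoint", contains both the Cox comparison and the Kaplan-Meier estimate.

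Section 11 calls itself an overview and leaves detail to the SAP. No supplied text names a competing-risk estimator.

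**The concern.** Kaplan-Meier with death censored treats a subject who has died as if a stroke could still follow at the same rate as in survivors. One minus Kaplan-Meier then describes risk in a hypothetical population in which nobody dies of anything else. Cumulative incidence is the proportion of patients who actually have the event by a given time. The two differ whenever subjects die event-free, and Kaplan-Meier is always the higher. The estimator named in the plan therefore does not estimate the quantity named.

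The setting makes this relevant. All subjects are 80 or older, each carries at least one added bleeding risk, and section 5.2.1 says "The planned mean duration of study treatment is 2 to 2.5 years".

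What is at stake is the absolute risk reported for each arm, and anything a reader takes from the curves. The plan announces no Kaplan-Meier risk difference or number needed to treat. One read from the curves would be overstated if event-free death is about equally frequent in the two arms.

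**Working it through.** **The plan's own figure.** Schoenfeld's formula with hazard ratio 0.5, two-sided 5%, 80% power and 1:1 allocation gives 4 × (1.960 + 0.842)² / (ln 0.5)² = 65.3. The 65 events in section 11.6 reproduce (power with 65 events is 79.8%). The count does not depend on the point raised here.

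**Inputs**
- Stroke/SEE rate λ: 0.05 per year on placebo and 0.025 on DU-176b (section 11.6: 5%/year, hazard ratio 0.5).
- Major bleeding rate: 0.0199 per year (section 5.2.1: 1.99%/year on 15 mg at age 80 or older).
- Time t: 2 and 2.5 years (section 5.2.1).
- Rate μ of death without a prior event: not in the documents; 0.02, 0.05, 0.10 and 0.15 per year assumed. This is not all-cause mortality: fatal strokes are events, and deaths after an event do not compete.
- For standard errors: 400 per arm, 2-year enrollment (assumed uniform) plus 1.5 years of follow-up (section 11.6), and no other withdrawal.

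**Formulas (constant rates)**
- One minus Kaplan-Meier, death censored: 1 − exp(−λt)
- Cumulative incidence: λ/(λ+μ) × [1 − exp(−(λ+μ)t)]
- Standard error (Greenwood): exp(−λt) × √{(1/400) ∫₀ᵗ λ / [exp(−(λ+μ)u) G(u)] du}, with G(u) = 1 up to 1.5 years and (3.5 − u)/2 after

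**Example.** Placebo, 2.5 years, μ = 0.10: Kaplan-Meier is 1 − exp(−0.125) = 11.75%. Cumulative incidence is (0.05/0.15) × [1 − exp(−0.375)] = 10.42%. The excess is 1.33 points.

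**Results at 2.5 years**

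| Quantity | Kaplan-Meier | Cumulative incidence, μ = 2 / 5 / 10 / 15% | Excess, points | Excess ÷ SE |
|---|---|---|---|---|
| Stroke/SEE, placebo | 11.75% | 11.47 / 11.06 / 10.42 / 9.84% | 0.28 / 0.69 / 1.33 / 1.91 | 0.16 / 0.38 / 0.71 / 0.99 |
| Stroke/SEE difference, equal μ | 5.69 points | 5.56 / 5.36 / 5.06 / 4.77 | 0.14 / 0.33 / 0.64 / 0.92 | 0.06 / 0.15 / 0.27 / 0.38 |
| Major bleeding, 1.99%/year | 4.85% | 4.73 / 4.56 / 4.30 / 4.05% | 0.12 / 0.29 / 0.55 / 0.80 | 0.10 / 0.24 / 0.45 / 0.62 |

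Standard errors behind the last column are 1.76 to 1.93 points for placebo, 2.19 to 2.41 for the difference and 1.17 to 1.29 for bleeding.

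**At 2 years**, placebo is 9.52% against 9.33 / 9.06 / 8.64 / 8.24%, an excess of 0.18 / 0.45 / 0.88 / 1.27 points (SE 1.51 to 1.62).

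**Later times.** The excess grows with time. At 15%/year it reaches 1.06 standard errors for placebo at 2.75 years and 1.10 at 3 years.

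**Unequal deaths.** The excess in the risk difference vanishes when the DU-176b rate of event-free death is about twice the placebo rate: 3.9 / 10.0 / 20.9 / 33.0% per year against placebo 2 / 5 / 10 / 15%.

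**Ratios and rates.** With equal μ = 10%, the 2.5-year risk ratio is 0.516 by Kaplan-Meier and 0.515 by cumulative incidence. In simulation, events per person-year stayed at 4.99 to 5.01% for stroke/SEE and 1.99 to 2.00% for bleeding at every assumed death rate.

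**The case against.** The strongest reply is that little depends on this. No planned test uses the curves. The Cox model with death censored is a valid cause-specific comparison, and Kaplan-Meier is its usual companion plot. At 2 and 2.5 years the excess stays below one standard error, and the risk ratio hardly moves. The size rests on a death rate the documents do not give. The exclusions in section 4.1.2 (current or recent malignancy, NYHA class 3 or above, dialysis) are some reason not to presume the top of the assumed range. The SAP may add a competing-risk estimate, and the endpoints that include all-cause death will show the mortality burden.

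Most of this stands, and it limits the point to descriptive estimates. It does not remove it. The excess is systematic, does not shrink with sample size and is not reflected in the confidence interval. The method is already named, so a SAP that follows the protocol repeats the mismatch. Composites that include death do not give the absolute risk of stroke/SEE.

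It is also fair that the extension to other endpoints is inferred. Analysis in the same way could mean the Cox comparison alone. The core point needs only sections 11.4.2.1.1 and 11.4.2.1.2.

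**Conclusion.** The concern holds. As written, the plan will overstate the cumulative incidence of stroke/SEE in each arm. The direction follows from the method and needs no assumption beyond some event-free deaths. The size does depend on assumption: for placebo at 2.5 years it is 0.28 to 1.91 points, a relative excess of about 2.5 to 20%, if event-free death runs at 2 to 15% per year with constant rates.

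On the natural reading of sections 11.4.2.2 and 11.4.5.1, the same applies to the bleeding categories and to secondary endpoints 1 (stroke, SEE, CV death) and 2 (MACE). For each, only deaths outside its own definition compete.

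Not affected are the Cox hazard ratio, the significance level, the 65 events and secondary endpoints 3 to 5, which include all-cause death. Section 1 says of bleeding that "clinical acceptability was also assessed with reference to the incidence of major bleeding with available oral anticoagulant therapies". No bias is claimed there, because the comparator figures are per-year rates and events per person-year are not inflated by censoring at death.

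**What to change.** In section 11.4.2.1.2, and in the SAP before unblinding, state that cumulative incidence for stroke/SEE, secondary endpoints 1 and 2 and the bleeding endpoints will be estimated by the Aalen-Johansen estimator, with death not counted in the endpoint as the competing event. Keep the Cox model as the primary test, and Kaplan-Meier for secondary endpoints 3 to 5. A Kaplan-Meier plot may stay beside the Cox result for the other endpoints, provided it is not labelled cumulative incidence.

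The cost is one sentence of analysis wording and standard software. Section 6.14 already collects deaths as CV or other cause. Significance level, power and event target do not change. The one downside is that reported absolute risks will be slightly lower.

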11.4.2.2 Secondary Endpoints

The following secondary endpoints will be analyzed in the same way as primary endpoints.

- 1) Composite of stroke, SEE, and death due to CV
- 2) MACE
- 3) Stroke, SEE, and all-cause mortality
- 4) Net clinical benefit: stroke, SEE, major bleeding, and all-cause mortality
- 5) All-cause mortality

11.4.2.3 Other Endpoints

The following other endpoints will be descriptively summarized.

- 1) Hospitalization due to CV condition (including hospitalizations for bleeding)
- 2) Modified Rankin Scale (approximately) 1 month after the onset of stroke
- 3) Stroke, SEE, and TIA
- 4) Number of occurrences of stroke and SEE
- 5) VTE (PTE and DVT)

11.4.2.4 Other Analysis Methods

Subgroup analysis using the major baseline subject characteristics (demographic and reference ranges) will be conducted for the primary endpoint. Details of subgroups will be specified in the Statistical Analysis Plan.

11.4.3 Pharmacokinetic Analysis

Summary statistics for plasma DU-176 concentration will be calculated at each blood sampling point, and a plot of the time course will be prepared.

11.4.4 Pharmacodynamic Analysis

Summary statistics for PD indicators (PT and aPTT) and biomarkers (D-dimer and F1+2) will be calculated at each blood sampling point, and the changes before and after administration (time course) will be plotted.

11.4.5 Safety Analysis

Unless otherwise stated, the safety analysis set will be used for safety analysis. The analysis period will be from the initiation of study treatment to the examination at completion of study treatment or the examination at discontinuation******. Serious adverse events observed during the period from the examination at completion of study treatment to the final follow-up examination and data obtained at the final follow-up examination will be tabulated separately, as necessary. Adverse events will be coded using the International Council for Harmonisation of Technical Requirements for Pharmaceuticals for Human Use (ICH) Medical Dictionary for Regulatory Activities (MedDRA), and system organ classes will be tabulated using MedDRA System Organ Classes, and adverse event terms will be tabulated using Preferred Terms.

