4.2.1.2 Follow-up Survey During Study Drug Interruption

The investigator or subinvestigator will survey the following items until the examination at completion of study treatment or until the resumption of treatment at the visit specified in "6. STUDY PROCEDURES" at least every 8 weeks at a visit or by telephone, and will enter the information on the case report form. If the subject cannot be contacted by

telephone, surveys will be performed by letter.

- 1) Whether any serious adverse events have occurred
- 2) Whether any efficacy events have occurred
- 3) Whether any bleeding events have occurred
- 4) Whether any of the following drugs (including over-the-counter drugs) have been used: anticoagulants, thrombolytic drugs, antiplatelet drugs, intravenous antiarrhythmic drugs, or acidic NSAIDs
- 5) Blood pressure and pulse rate (only if the subject makes a visit)
- 6) Laboratory tests determined to be appropriate by the investigator or subinvestigator (only if the subject makes a visit). However, if warfarin is being administered, measurement of PT-INR is mandatory.

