6.8 Laboratory Tests

Blood samples and urine samples for laboratory tests will be collected at the eligibility assessment examination, once every 8 weeks during the study treatment period (from Week 4 to Week 48, at Visit 3, Visit 5, Visit 7, Visit 9, Visit 11, and Visit 13/from Week 48 onward, at Visit 14, Visit 15, Visit 16...), the examination at completion of study

treatment, and the final follow-up examination or the examination at discontinuation. §§§
All laboratory tests will be performed as a batch by SRL, Inc.

- 1) Hematology test
 - Red blood cell count, hemoglobin, hematocrit, white blood cell count, white blood cell differentials (neutrophils, lymphocytes, monocytes, eosinophils, and basophils), platelet count, and PT-INR*
 - *: PT-INR will be measured if the subject received warfarin within the 8 weeks prior to the day of informed consent, or if the subject is receiving warfarin during study drug interruption or during the follow-up after study drug discontinuation.
- 2) Blood chemistry test
 - Total protein, albumin, total bilirubin, direct and indirect bilirubin, ** AST, ALT, ALP, GGT, LDH, CK, BUN, creatinine, uric acid, Na, K, Cl, total cholesterol, triglyceride **: Direct and indirect assays will be performed when total bilirubin ≥ 2 mg/dL
- Endocrinology tests
 Troponin I, human brain natriuretic peptide (BNP)
- 4) Urinalysis

Urine glucose, urine protein, urine blood, urinary sediment (red blood cells)

If the subject makes visits during study drug interruption or after study drug
discontinuation, measurement of laboratory test items the investigator or subinvestigator
considers suitable (if warfarin is being administered, PT-INR is mandatory) will be
requested, and the dates when specimens were collected will be entered on case report
forms.

If any abnormal laboratory data (deviations from reference ranges) are observed, the investigator or subinvestigator will assess whether to handle these data as an adverse event, and if they are considered to be adverse events, they will be entered in the adverse event field of the case report form.

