9.1 Bleeding Events

Bleeding-related adverse events observed between the initiation of study treatment and the examination at completion of study treatment or the examination at discontinuation the discontinuation will be assessed as bleeding events. Bleeding events will be reassessed by a Clinical Bleeding Event Committee independent of the assessment of the investigator or subinvestigator, and the assessment of the Clinical Bleeding Event Committee will be taken as the final assessment.

Bleeding events will be classified into major bleeding, clinically relevant non-major bleeding, and minor bleeding according to the following definitions. Detailed definitions of bleeding events are shown separately in "Procedures for the Clinical Bleeding Event Committee."

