11.4.5.2 Adverse Events

Incidences of adverse events will be calculated by treatment group. Frequencies of adverse events will also be tabulated by event and by severity. Adverse drug reactions will be analyzed in the same way.

In tabulation by System Organ Class or Preferred Term, if multiple adverse events with the same System Organ Class or Preferred Term occur in the same subject, these will be counted as a single event. System Organ Classes will be displayed in the internationally agreed order, and Preferred Terms will be displayed in code order. In this study, adverse events that occur after the initiation of study treatment (treatment emergent adverse events [TEAEs]) will be tabulated.

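### Does the single all-follow-up safety period leave it unclear whether major bleeding is also analysed on treatment?

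*Combined protocol and SAP*

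**What the plan says.** Section 11.4.5 sets the set and the period for safety. On the set: "Unless otherwise stated, the safety analysis set will be used for safety analysis". On the period: "The analysis period will be from the initiation of study treatment to the examination at completion of study treatment or the examination at discontinuation", with a footnote confining the discontinuation examination to subjects who withdraw from the study itself. Section 9.1 uses the same span to define which bleeds are assessed.

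Section 11.4.5.1 gives the method by cross-reference: "Bleeding events will be classified into the following categories and summarized by treatment group, and analyzed in the same way as the primary endpoint". It names neither a window nor a set.

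The method referred to is in section 11.4.2.1 (Primary Endpoint), which has two parts. Section 11.4.2.1.1 is a Cox model adjusted for CHADS₂ stratum, and of the events it counts it says: "This will apply to all events whether or not the subject receives the study drug". Section 11.4.2.1.2 adds Kaplan-Meier curves and a sensitivity analysis limited to time on treatment plus 3 days after the last dose, with subjects at risk again if they resume. It names the mITT set and the PPS.

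Subjects who stop drug but stay in the study are still asked about bleeding at least every 8 weeks (sections 4.2.1.2, 4.2.2.2 and 6.15). The ban on anticoagulants in section 5.3.1 does not cover those periods, and section 4.2.1.2 foresees their use: "if warfarin is being administered, measurement of PT-INR is mandatory".

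**The concern.** Read alone, the safety section offers one window for major bleeding, and that window mixes time on study drug with time off it. A subject who stopped early contributes months in which a bleed cannot be due to the study drug, and some of that time may be spent on warfarin or another anticoagulant. If the drug raises bleeding, off-drug time pulls the hazard ratio towards 1. Off-drug anticoagulant use that differs by arm could move it either way.

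The protocol sets no margin for major bleeding. Section 1 says it is compared with placebo and its clinical acceptability judged with reference to rates on available anticoagulants. A reader of one rate or ratio would need to know its window. If the on-treatment run were not planned for bleeding, or its set not fixed, the choice might be made after results were seen.

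**Working it through.** **1. What the cross-reference brings in.**

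- Section 11.4.5.1 points to the primary endpoint, not to the primary analysis. The protocol treats these as different things: Primary Endpoint is the title of 11.4.2.1, Primary Analysis that of 11.4.2.1.1 alone, and section 11.5 uses the narrower term when it restricts changes.
- Section 11.4.2.2 uses the same shorthand for the secondary efficacy endpoints. An analyst would read both references alike: all-events analysis first, on-treatment run second.
- The single period in 11.4.5 does not conflict with this. Section 11.4.2.1.1 also states one all-follow-up period for efficacy, and 11.4.2.1.2 then adds the narrower window as a sensitivity analysis.

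**2. Which set.** The default in 11.4.5 gives the safety analysis set. Sections 11.2.1.2 and 11.2.4 show that mITT and the safety set have the same members (at least one tablet) and the same time origin (first dose). They differ only in where a subject given the wrong treatment throughout is counted. Only a PPS run would differ materially, and the default points away from it.

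**3. Size.** The plan has no figure of its own for this point; its 65 events concern efficacy. Inputs:

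- Major bleeding on 15 mg at age 80 or older: 1.99%/year (section 1).
- Placebo rate: not given; 1.0%/year assumed.
- Follow-up: 2 years' enrolment plus 1.5 years (section 11.6). With uniform entry this runs from 1.5 to 3.5 years, mean (1.5 + 3.5)/2 = 2.5. With 400 per arm, 400 × 2.5 = 1000 patient-years per arm, ignoring deaths and losses.
- Off-drug share f: not given. Section 5.2.1 plans a mean of 2 to 2.5 years on treatment, so f is about 1 − 2.5/2.5 = 0 to 1 − 2/2.5 = 20%; 30% is added as a stress case.
- Off-drug bleeding rate: placebo rate in both arms, with no other anticoagulant.

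All-follow-up rate on edoxaban = (1 − f) × 1.99 + f × 1.0. Dividing by 1.0 gives the hazard ratio.

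| f | Edoxaban, %/year | Hazard ratio | Difference per 100 patient-years |
|---|---|---|---|
| 0 | 1.99 | 1.99 | 0.99 |
| 10% | 1.791 + 0.1 = 1.89 | 1.89 | 0.89 |
| 20% | 1.592 + 0.2 = 1.79 | 1.79 | 0.79 |
| 30% | 1.393 + 0.3 = 1.69 | 1.69 | 0.69 |

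To vary the placebo assumption at f = 20%, use HR × 0.8 + 0.2. An on-treatment ratio of 1.5 becomes 1.40, 2.0 becomes 1.80 and 3.0 becomes 2.60.

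**4. Against sampling error, at f = 20%.** The 95% interval is HR × exp(±1.96 × √(1/n₁ + 1/n₂)).

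- All follow-up: 17.9 v 10.0 bleeds. √(1/17.9 + 1/10.0) = 0.395, so 1.79 (0.83 to 3.88).
- On treatment: 800 × 1.99% = 15.9 v 800 × 1.0% = 8.0 bleeds. √(1/15.9 + 1/8.0) = 0.433, so 1.99 (0.85 to 4.65).
- Off drug: 200 × 1.0% = 2.0 bleeds per arm.

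**5. Against the reference rates.** For age 80 or older, section 1 gives 4.28%/year on dosage-adjusted edoxaban 30 mg and 6.77%/year on warfarin. The window moves the 15 mg rate by 1.99 − 1.79 = 0.20; the gap to the nearer reference is 4.28 − 1.99 = 2.29.

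**The case for a change.** The cross-reference cannot be applied word for word. The primary endpoint is analysed by ITT from randomization, whereas safety uses the safety set from first dose, so some features must be replaced and section 11.4.5.1 does not list them. Three readings are possible: the Cox model over the 11.4.5 period only; that plus an on-treatment run in the safety set; or that plus runs in mITT and PPS. For the primary safety endpoint one explicit sentence would be tidier, it would cost little, and the data are already collected.

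All of that stands as a comment on wording. It does not show that following the plan gives a wrong answer. Section 11.4.5 itself says which features are replaced, namely set and period, and the second reading is the ordinary one. Even the narrowest reading leaves a valid comparison of bleeding under the treatment strategies as followed, and that analysis belongs in the report in any case. The on-treatment run is not the cleaner of the two: section 4.2.1.1 allows interruption after an adverse event, and section 9.1.2 makes stopping drug on a physician's instruction one marker of clinically relevant non-major bleeding, so censoring at drug stop may be informative.

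The worry about a late choice of window is met by section 5.2.2.4, under which the analysis plan must be final before unblinding. Section 11 calls itself an overview and leaves detail to a Statistical Analysis Plan. That plan's text is not in the document reviewed, so whether it already names window and set cannot be checked.

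**Conclusion.** No change to the plan follows. The wording leaves a small gap that an analyst fills sensibly: the all-follow-up Cox analysis over the section 11.4.5 period, with the on-treatment run of section 11.4.2.1.2 beside it in the safety analysis set. Interruption and resumption dates (6.3), off-drug anticoagulant use (6.4) and off-drug bleeding (6.15) are recorded, so both can be produced.

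On the illustrative inputs the choice of window moves the hazard ratio from 1.99 to between 1.89 and 1.79 for 10 to 20% of follow-up off drug. At 20% it involves about 2 bleeds per arm, with intervals that overlap almost entirely. These figures rest on an assumed placebo rate, an assumed off-drug share and no off-drug anticoagulant use. The last could shift the ratio in either direction, so the documents do not fix the sign of the difference. No endpoint, test or decision rule depends on it.
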